9.7. Data analysis

The study population of Pfizer-BioNTech COVID-19 mRNA vaccine recipients will be described in terms of demographic characteristics (age, gender, ethnicity, occupation) and medical history characteristics outlined in [Section 9.4.1](#). Vaccination characteristics, including number of doses received and interval between doses, will also be described.

The incidence rates of medically attended safety events of interest and corresponding 95% Poisson exact confidence intervals (95% CI) will be estimated in the primary safety dataset of participants who enroll within 2 days of vaccination. Rates will also be estimated for the overall study population and within subcohorts of interest such as pregnant vaccine recipients, immunocompromised participants, and within age-categories.

A final analysis will also be conducted for the following subcohorts of interest, given the potential for mixed exposure:

1. **Pfizer-BioNTech vaccine only**: all participants who only receive Pfizer-BioNTech COVID-19 mRNA vaccine(s), and no other COVID-19 vaccine(s), prior to index date and during their follow-up period.
2. **Heterologous vaccination**:
 - a) **Pfizer-BioNTech booster(s) only**: all participants who received only Pfizer-BioNTech COVID-19 mRNA vaccine dose(s) as booster dose(s) during the study period, but where the primary vaccine course (prior to index date) was non-Pfizer-BioNTech.
 - b) **Heterologous primary course**: all participants who received Pfizer-BioNTech COVID-19 mRNA vaccine as a first dose at index date, and then received a non-Pfizer-BioNTech second dose during their follow-up period. No booster doses were received.
 - c) **Other combination heterologous vaccine course/booster**: all participants with a heterologous primary course and/or heterologous booster dose(s), who do not fit the criteria for inclusion in subcohorts 2(a)-(b) above.

It is anticipated that rates will be reported for the following intervals, overall and for each of the subcohorts of interest:

- Follow-up at weeks 1, 2, 4, 6 and 8 following a Pfizer-BioNTech COVID-19 mRNA vaccine dose,
- Quarterly follow-up following a Pfizer-BioNTech COVID-19 mRNA vaccine dose (until 24 months following index date vaccine dose, or end of study, whichever occurs first).

[figure not shown]

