Time at risk will be assessed from the Pfizer-BioNTech COVID-19 mRNA vaccine dose until the subsequent follow-up time point or until the next Pfizer-BioNTech COVID-19 mRNA vaccine dose received, death, withdrawal of consent, loss to follow-up, 24 months or end of study period, whichever occurs first. Sensitivity analysis may be conducted with censoring at any COVID-19 vaccine dose received.

All cases of reported laboratory confirmed COVID-19 in the study population will be described by the Brighton Collaboration “Vaccine-associated Enhanced Disease” Working Group case definitions for COVID-19 VAED.

Counts of newly reported medically attended safety events of interest and counts of vaccinated participants will be summarized as per the intervals above. Counts will be summarized by whether medical validation of the event was possible, or not.

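### Vaccine subcohorts that depend on doses received after index give 2(b) and part of 2(c) death-free time and place early deaths in the Pfizer-BioNTech-only subcohort

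*Protocol*

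**What the plan says.** Protocol section 9.7 plans a final analysis in vaccine subcohorts because exposure may be mixed.

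- **Pfizer-BioNTech only:** "all participants who only receive Pfizer-BioNTech COVID-19 mRNA vaccine(s), and no other COVID-19 vaccine(s), prior to index date and during their follow-up period".
- **2(a), Pfizer-BioNTech booster(s) only:** Pfizer-BioNTech boosters during the study, "but where the primary vaccine course (prior to index date) was non-Pfizer-BioNTech".
- **2(b), heterologous primary course:** a Pfizer-BioNTech first dose at index; the participant "then received a non-Pfizer-BioNTech second dose during their follow-up period. No booster doses were received".
- **2(c), other combinations:** "all participants with a heterologous primary course and/or heterologous booster dose(s), who do not fit the criteria for inclusion in subcohorts 2(a)-(b) above".

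Rates are anticipated for each subcohort at weeks 1, 2, 4, 6 and 8 after a Pfizer-BioNTech dose, and quarterly after that. On person-time the section says: "Time at risk will be assessed from the Pfizer-BioNTech COVID-19 mRNA vaccine dose until the subsequent follow-up time point". Counting stops sooner if the participant has a further Pfizer-BioNTech dose, dies, withdraws, is lost, or reaches month 24 or the study's end. A dose from another manufacturer does not end time at risk in the main analysis. The one related provision is optional: "Sensitivity analysis may be conducted with censoring at any COVID-19 vaccine dose received".

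Death is a listed safety event (section 9.3.1, Table 2) and an outcome variable (section 9.3, Table 1). Section 9.9 concedes that attributing outcomes to an exposure period may be hard, but does not mention grouping participants by doses they have yet to receive.

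**The concern.** Membership of the Pfizer-BioNTech-only subcohort, of 2(b), and of 2(c) where the other-manufacturer dose follows index is known only after later doses have or have not been given. The clock starts earlier, at the Pfizer-BioNTech dose. A participant has to be alive and in the study at the second dose to belong to 2(b), so the time before that dose adds to the 2(b) denominator but can add no death to its numerator. Someone who would have switched but died or left first is counted as Pfizer-BioNTech only. The requirement of no booster in 2(b) selects on the future a second time: a 2(b) member who reaches a booster moves to 2(c).

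At stake are subcohort rates that differ by manufacturer history when nothing differs in truth. The early windows are worst affected, and those are the ones a vaccine-safety reader looks at first.

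**Working it through.** **Plan's own figure.** The protocol gives no number for the vaccine subcohorts: no share switching, no dose gap, no expected rate. Its enrolment target reproduces (10,000 / 0.75 = 13,333.3, rounded up to 13,334), but nothing below depends on it.

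**Which groups are affected.**

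| Subcohort | When membership is settled | Death-free time counted? |
|---|---|---|
| Pfizer-BioNTech only | End of follow-up | No, but receives deaths before a switch |
| 2(a) | At index, apart from no other-manufacturer dose following | No |
| 2(b) | At the second dose, then again if a booster follows | Yes |
| 2(c), already heterologous at index | At index | No |
| 2(c), other-manufacturer dose after index | At that dose | Yes |

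**Model for death.** The inputs are assumptions: constant death rate λ = 0.01 per year (100 per 10,000 person-years) in everyone, share s = 20% of first-dose starters due a non-Pfizer-BioNTech second dose at gap g, horizon T = 2 years, no dropout and no further Pfizer-BioNTech dose. Per starter:

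- 2(b) deaths = s(e^(−λg) − e^(−λT))
- 2(b) person-years = s[g·e^(−λg) + (e^(−λg) − e^(−λT))/λ]
- All deaths = 1 − e^(−λT); all person-years = (1 − e^(−λT))/λ
- Pfizer-BioNTech only = all minus 2(b)

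*Example, g = 6 weeks = 0.11499 years.* e^(−λg) = 0.998851 and e^(−λT) = 0.980199.

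- 2(b): deaths 0.2 × 0.018652 = 0.003730; person-years 0.2 × (0.11486 + 1.86521) = 0.39601; rate 94.2 per 10,000.
- Pfizer-BioNTech only: deaths 0.019801 − 0.003730 = 0.016071; person-years 1.98013 − 0.39601 = 1.58412; rate 101.5.
- Ratio 0.93; the truth is 1.

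Rates per 10,000 person-years, 2(b) vs Pfizer-BioNTech only:

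| Gap | 24 months | Ratio | Cumulative to week 12 | Ratio |
|---|---|---|---|---|
| 3 weeks | 97.1 vs 100.7 | 0.96 | 75.0 vs 106.3 | 0.71 |
| 6 weeks | 94.2 vs 101.5 | 0.93 | 50.0 vs 112.5 | 0.44 |
| 12 weeks | 88.4 vs 102.9 | 0.86 | 0 vs 125.0 | 0 |
| 26 weeks | 74.9 vs 106.3 | 0.71 | 0 vs 124.9 | 0 |

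For true rates from 50 to 200 per 10,000 the ratios hardly move. At a 6-week gap, s from 5% to 50% takes the 24-month ratio from 0.94 to 0.89.

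**Non-fatal events.** Let a first event before g change the chance of switching from s to q. With E = 1 − e^(−λg) the early events and L = e^(−λg) − e^(−λT) the later ones, 2(b) has qE + sL events, and its person-time is weighted in the same way. For λ = 0.01, g = 6 weeks and s = 10%:

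| Effect of an early event | q | Ratio, 24 months | Ratio, to week 12 |
|---|---|---|---|
| Stops the switch | 0 | 0.94 | 0.47 |
| None | 10% | 1.00 | 1.00 |
| Doubles switching | 20% | 1.07 | 1.59 |
| Half switch | 50% | 1.27 | 3.85 |

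**Does the optional sensitivity analysis help?** It moves the censoring date and leaves group assignment alone. Ending 2(b) time at the other-manufacturer dose keeps only the period in which a 2(b) member cannot die, so the 2(b) death rate becomes zero.

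**Check of the fix** (g = 6 weeks). Split at the switch, the heterologous state has 0.003730 deaths in 0.2 × 1.86521 = 0.37304 person-years, and the Pfizer-only-so-far state has 0.016071 in 1.98013 − 0.37304 = 1.60709. Both rates are 100.0 and the ratio is 1.00.

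**The case against.** The strongest reply concerns weight. Section 9.5 calls the secondary analyses exploratory, without formal testing, and section 9.7 plans separate rates with confidence intervals and no contrast between vaccine subcohorts. The primary safety dataset and overall rates do not use the assignment. All of this stands and limits severity. It does not remove the fault, because each affected rate is distorted on its own and the rates will be set side by side.

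Four stronger readings are tempting, and the protocol does not support them:

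- *All heterologous groups carry immortal time.* Subcohort 2(a) is heterologous through a primary course finished before index, and 2(c) can include people with a mixed primary course who enrol at a Pfizer-BioNTech booster. Their early deaths stay in their own groups. With enrolment opened to booster doses, these participants may be numerous, though no split is given.
- *Early events in general move to Pfizer-BioNTech only.* That is certain for death and for leaving before a switch. Most events in Table 2 need not be fatal, and for non-fatal events the bias can run either way.
- *The distortion is typically around 0.7.* Over 24 months that needs an assumed gap of about six months, whereas 2(b) concerns the second dose of a primary course.
- *Censoring at any COVID-19 dose should become the main rule.* This is a separate trade-off. Keeping later time fits the real-world and 24-month aims in sections 7.2 and 9.9, and censoring there would remove the post-switch time that the heterologous state needs.

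**Conclusion.** The point holds for the Pfizer-BioNTech-only subcohort, for 2(b), and for members of 2(c) whose other-manufacturer dose follows index. Followed as written, section 9.7 yields a 2(b) death rate of zero in any reporting window that closes before the second dose. With the assumed 20% switching, it overstates the Pfizer-BioNTech-only death rate by about 1 to 6% over 24 months and 6 to 25% to week 12, across gaps of 3 to 26 weeks. The zero follows from the definitions alone. The other sizes rest on the assumed share, gap and constant rate, and on ignoring dropout and further doses. For non-fatal events no direction can be claimed. The subcohort definitions are fixed in the protocol itself, so this is not a detail left to a statistical analysis plan. Given the exploratory status of these rates, it should be fixed, but it does not threaten the primary objective.

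**What to change.** In section 9.7, define the vaccine subcohorts by time-varying history. Split each participant's person-time at every COVID-19 dose of any manufacturer, and assign events and time to the history up to that date: Pfizer-BioNTech only so far until the first other-manufacturer dose, and the relevant heterologous state from then on. Keep post-switch time in the heterologous state. Replace the no-booster condition in 2(b) with a change of state at the booster date. Participants already heterologous at index start in that state.

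Date and manufacturer of prior and subsequent doses are already collected (sections 9.4.1 and 9.4.3), so the cost is wording and programming. The heterologous groups lose their pre-switch person-time: in the 6-week example, 0.39601 − 0.37304 = 0.02297 of 0.39601, or about 6% of the 2(b) total. That time moves to the Pfizer-only-so-far state.

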9.3. Variables

The key vaccine exposure, baseline, and safety outcome variables are listed in Table 1. Detailed definitions are provided in [Section 9.3.1](#).

Table 1. Key vaccine exposure, baseline, and safety outcome variables to be collected in this study

Variable	Role	Data Source(s) ^a
Date of index date dose COVID-19 vaccination	Exposure	Participant and/or their designee
Location where index date dose COVID-19 vaccine was administered	Exposure	Participant and/or their designee
Vaccine lot number (index date dose)	Exposure	Participant and/or their designee
Anatomical site where index date dose COVID-19 vaccine was administered	Exposure	Participant and/or their designee
Date of all subsequent dose(s) COVID-19 vaccination(s)	Exposure	Participant and/or their designee
Location where all subsequent COVID-19 vaccine dose(s) was/were administered	Exposure	Participant and/or their designee
Vaccine lot number (all subsequent doses)	Exposure	Participant and/or their designee

090177e1991e3913Approved\Approved On: 18-Jan-2022 22:29 (GMT)

Table 1. Key vaccine exposure, baseline, and safety outcome variables to be collected in this study

Variable	Role	Data Source(s)^a
Anatomical site where all subsequent COVID-19 vaccine(s) was/were administered	Exposure	Participant and/or their designee
Demographics	Baseline characteristics	Participant and/or their designee
Medical History	Baseline characteristics	Participant and/or their designee
Employment characteristics	Baseline characteristics	Participant
Concomitant medications and other vaccines	Baseline characteristics	Participant and/or their designee
Participant reported safety event of interest (described in Section 9.3.1)	Outcome	Participant and/or their designee
Validated safety event of interest	Outcome	Health care provider (HCP) questionnaire or medical record review
Participant reported hospitalization (date and length of admission)	Outcome	Participant and/or their designee
Validated hospitalization (date and length of admission)	Outcome	Health care provider questionnaire or medical record review
Participant's designee reported death (date)	Outcome	Participant's designee
Validated death (date)	Outcome	Health care provider questionnaire or medical record review
Pregnancy status and last menstrual period (LMP) (if applicable)	Baseline characteristics	Participant, their designee, or medical record review

090177e1991e3913\Approved\Approved On: 18-Jan-2022 22:29 (GMT)

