
Primary study objective:
 
Estimate the real-world incidence of medically attended safety events of interest and other clinically significant events among individuals vaccinated with the Pfizer-BioNTech COVID-19 mRNA vaccine after approval in the EU.
	
Medically attended safety events of interest, and other clinically significant events
	
Incidence rates per 10,000 person-years and corresponding 95% Poisson exact CI. Incidence rates precision estimates as provided in Section 9.5.

Secondary objective:
 
Evaluate whether the vaccine recipients experience increased risk of medically attended safety events of interest post-vaccination, via comparison with expected background rates and, as feasible, by self-controlled risk interval (SCRI) analysis.
	
Medically attended safety events of interest
	
OE analysis: Safety event of interest (observed) incidence rates in cohort of study participants compared to background (expected) incidence rates, obtained from the EMA-funded COVID-19 vaccine monitoring ACCESS program or, if unavailable, from historical or concurrent rates reported in the literature.
 
SCRI analysis: Incidence rate ratio (IRR) of medically attended safety events of interest occurring in the risk interval versus the control period, estimated by conditional Poisson regression models. Sensitivity analysis for SCRI: considering different lengths of the risk and control intervals.

090177e1991e3913\Approved\Approved On: 18-Jan-2022 22:29 (GMT)

Table 5. Planned analysis by study objective

Objective	Outcome of interest	Planned analysis

Secondary objective:
 
Estimate the incidence rates of medically attended safety events of interest among sub-cohorts of interest such as pregnant vaccine recipients, immunocompromised participants, and stratified by age.
	
Medically attended safety events of interest
	
Incidence rates per 10,000 person-years and corresponding exact Poisson 95%CI*:
 
 • Among sub-cohort of pregnant vaccine recipients, • Among sub-cohort of immunocompromised participants, • Stratified by age: 18-29; 30-39; 40-49; 50-59; 60-69; 70-79; 80 and above.

European Union (EU); 95% Poisson exact confidence intervals (95% CI); self-controlled risk interval (SCRI); incidence rate ratio (IRR).

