18.1.1. Baseline questionnaire (index date dose)

- Informed consent
- Age in years (autocalculated based on date of birth, where possible)
- Sex (male/female)
- Ethnicity/Race
- Occupation (sector, e.g. Health & Social Care)
- Medical history
 - Height/Weight
 - Current conditions (*select all that apply*)
 - Asthma
 - Chronic cardiac disease
 - Chronic hematological disease
 - Chronic kidney disease
 - Chronic neurological disorder
 - Chronic obstructive pulmonary disease (COPD)
 - Congestive heart failure
 - Dementia
 - Diabetes
 - HIV/AIDS
 - Immunocompromised (any cause)
 - Solid tumour (localized or metastatic)
 - Leukemia
 - Lymphoma
 - Liver disease
 - Rheumatological disorder
 - Other (specify) (*medDRA coded*)

- How would you rate your health on a scale of 0-10?
- Frailty (Prisma 7 Questions⁶) (*patients age 65+ years only*)
 - Are you more than 85 years? (*this question will be filled from previous responses*)
 - Male? (*this question will be filled from previous responses*)
 - In general, do you have any health problems that require you to limit your activities?
 - Do you need someone to help you on a regular basis?
 - In general, do you have any health problems that require you to stay at home?
 - In case of need can you count on someone close to you?
 - Do you regularly use a stick, walker or wheelchair to get about?
- Any concomitant medication taken within 7 days prior to vaccination (*Drugbank coded*)
- Any prior COVID-19 vaccinations
 - Date of vaccination
 - Dose number
 - Manufacturer
- Any vaccinations (other than the COVID-19 vaccine) in the last 6 months
- Allergies to medication
- Prior infection with test-confirmed SARS-CoV-2 / COVID-19 disease
- Presence of potential active viral disease within previous 3 days prior to vaccination (e.g. fever, symptoms of cold, flu, or other inflammatory/infectious process)
- Pregnancy status (female participants of childbearing potential only)
- Vaccination information (of index dose):
 - Date of vaccination
 - Location (i.e. vaccination center)
 - Vaccine lot number
 - Anatomical site where vaccine was administered (i.e. which arm)
- Contact information for:
 - The participant
 - A secondary contact for the participant [for follow-up purposes only]
 - Primary care physician [for safety follow-up]
- Preferred participant follow-up method – telephone interview or web/app-based questionnaire

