18.1.4. Pregnancy outcomes questionnaire (as applicable)

- Self-reported pregnancy outcome:
 - Spontaneous abortion (miscarriage) (≤ 20 gestational weeks)
 - Elective or therapeutic termination
 - Live birth
 - Stillbirth (>20 gestational weeks, prior to delivery)
 - Ectopic pregnancy (a pregnancy outside the uterus)
 - Molar pregnancy (a non-viable fertilized egg implants in the uterus)
- Date of pregnancy outcome
- Gestational age at pregnancy outcome (weeks)

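### Rates for pregnant recipients are not split at the end of pregnancy, so those from about 12 months on mostly count post-pregnancy time

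*Protocol*

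**What the plan says.** Section 9.7 of the protocol gives a single rule for time at risk: "Time at risk will be assessed from the Pfizer-BioNTech COVID-19 mRNA vaccine dose until the subsequent follow-up time point or until the next Pfizer-BioNTech" dose. The remaining stops are "death, withdrawal of consent, loss to follow-up, 24 months or end of study period, whichever occurs first". End of pregnancy is not among them. The only variation offered concerns other vaccines: "Sensitivity analysis may be conducted with censoring at any COVID-19 vaccine dose received".

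The same section names pregnant recipients as a subcohort and then states: "It is anticipated that rates will be reported for the following intervals, overall and for each of the subcohorts of interest". The intervals are weeks 1, 2, 4, 6 and 8 after a Pfizer-BioNTech dose, and quarterly up to 24 months after the index date. Table 5 plans rates per 10,000 person-years "Among sub-cohort of pregnant vaccine recipients", without a separate rule.

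On data, the pregnancy outcomes questionnaire (18.1.4) collects "Date of pregnancy outcome" and gestational age at outcome. Table 1 (section 9.3) lists "Pregnancy status and last menstrual period (LMP) (if applicable" as a baseline variable. The baseline questionnaire (18.1.1) has only "Pregnancy status (female participants of childbearing potential only" and no LMP item; section 9.4.1 and the subsequent-dose questionnaire (18.1.2) are the same in this respect.

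**The concern.** Pregnancy differs from the other subcohort characteristics because it ends within about 40 weeks, while follow-up runs to 24 months. Under the rule as written, a woman pregnant at her dose keeps adding person-time and events to the pregnant row long after the pregnancy is over. For events whose risk changes during pregnancy (Table 2 includes deep vein thrombosis and pulmonary embolus), an excess confined to pregnancy would be averaged with later, non-pregnant time.

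Section 7.1 notes that pregnant individuals were not included in the pivotal study, and section 8 names them in a secondary objective, so readers will look to this row for information on pregnancy.

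The protocol also does not say whether membership is fixed by pregnancy at the dose or extends to pregnancies that begin later. A woman can be pregnant at one Pfizer-BioNTech dose and not at the next.

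**Working it through.** **The plan's own figures.** The protocol states no person-time figure for the pregnant subcohort, so there is none to reproduce. The enrolment target (10,000/0.75 = 13,334 rounded up) reproduces but does not bear on this point.

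**Inputs.** From the protocol: maximum follow-up of 24 months = 104.4 weeks; the intervals in 9.7; end of data collection on 31 October 2023 (section 6); attrition of 25 to 55% (Table 4). Assumed, because the protocol gives neither: pregnancy length L = 40 weeks (range 38 to 42) and gestational week at the dose, g, uniform from 0 to L.

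**Cumulative share.** Over H weeks from the dose, pregnant share = E[min(L − g, H)]/H. With g uniform this is 1 − H/(2L) for H ≤ L, and L/(2H) for H > L. With L = 40:

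| Time since dose | Calculation | Pregnant share |
|---|---|---|
| Week 1 | 1 − 1/80 | 99% |
| Week 8 | 1 − 8/80 | 90% |
| Week 12 | 1 − 12/80 | 85% |
| 6 months (26 weeks) | 1 − 26/80 | 67.5% |
| 9 months (39 weeks) | 1 − 39/80 | 51% |
| 12 months (52 weeks) | 20/52 | 38.5% |
| 18 months (78 weeks) | 20/78 | 26% |
| 24 months (104.4 weeks) | 20/104.4 | 19% |

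At 24 months the ceiling (dose at week 0, full follow-up) is 40/104.4 = 38%. For L = 38 to 42 the mean is 18 to 20% and the ceiling 36 to 40%.

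**Timing of vaccination.** For doses at weeks 4 to 13, mean remaining pregnancy is 31.5 weeks. The share is then 31.5/52 = 61% at 12 months and 31.5/104.4 = 30% at 24 months, falling below half only after 63 weeks. For doses at weeks 28 to 40 it is 67% at week 8, 50% at week 12 and 6% at 24 months.

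**Separate intervals.** If each quarter is instead a stand-alone interval from week a to week b (b ≤ 40), the share is 1 − (a + b)/80: 51% for weeks 13 to 26 and 19% for weeks 26 to 39. Any interval starting after week 40, which includes the four quarters from month 12 to month 24, has no pregnant time from women pregnant at the dose.

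**Shorter follow-up.** With constant-hazard attrition d over 24 months, the ceiling is [1 − (1 − d)^(40/104.4)]/d: 42% for d = 0.25 and 48% for d = 0.55. The corresponding means are 21% and 25%. If follow-up is cut at 31 October 2023, entry on 18 January 2022 leaves 93 weeks (mean 20/93 = 22%, ceiling 40/93 = 43%). Entry on 30 June 2022 leaves 69.7 weeks (mean 29%, ceiling 57%).

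**Dilution, for illustration only.** If the rate in pregnancy is RR times the rate afterwards, the 24-month rate is 1 + 0.192(RR − 1) times the post-pregnancy rate. RR = 2 gives 1.19, which is 40% below the pregnancy rate (1.19/2 = 0.60). RR = 4 gives 1.58, which is 61% below (1.58/4 = 0.39). The rate ratios have no source in the protocol.

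**The case against.** The strongest reply is that the secondary objective concerns recipients who are pregnant, not rates during pregnancy. Following them after delivery fits that wording and the long-term aim in section 9.9. A reader might infer that the pregnancy objective goes unanswered; the protocol does not support that. The week 1 to 8 rates are planned for this subcohort and are almost wholly pregnant time under even timing. This part of the objection stands.

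It also stands that 38% is not a bound for the study as it will run, since attrition and late entry raise it and a further Pfizer-BioNTech dose restarts the clock. The 40% and 61% figures rest on assumed rate ratios, apply to one 24-month rate, and give all post-pregnancy time the lower rate. If risk stays raised just after pregnancy, they overstate the dilution.

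On LMP, a reader might infer that gestation at the dose will be unknown. That goes too far. Table 1 allows medical records as a source, Annex 3 is a summary, and where an outcome is reported gestation at the dose follows from the outcome date and gestational age. What remains is a mismatch between Table 1 and the listed forms, which matters for pregnancies without a reported outcome.

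Finally, splitting person-time could be left to the statistical analysis plan, which is not at hand. But section 9.7 is not silent: it states the stops and applies the intervals to every subcohort. The closing text of 9.7 lets the analysis plan modify the protocol, so a correction there is possible but not assured.

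**Conclusion.** The concern holds for the later rates. Followed as written, section 9.7 yields cumulative rates for women pregnant at the dose that are mostly post-pregnancy time from about 12 months on, with about 19% pregnant time on average at 24 months. Quarterly intervals starting after about week 40 contain none. The early rates are sound, at about 90 to 99% pregnant time through week 8.

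These figures assume a 40-week pregnancy, vaccination spread evenly over gestation and full follow-up. For doses at weeks 4 to 13 the change to mostly post-pregnancy time comes at about 63 weeks instead of before 12 months. In the attrition scenarios, and for entry by early 2022, post-pregnancy time remains the majority at the end of follow-up whatever the gestation at the dose. For entry around mid-2022 that is true on average but not for every woman. The direction of the dilution is clear for an excess confined to pregnancy; its size cannot be fixed from the protocol.

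**What to change.** - In section 9.7 and Table 5, define the subcohort by pregnancy at the Pfizer-BioNTech dose that starts the interval.
- Split its person-time and events at the date of pregnancy outcome (18.1.4). Report during-pregnancy and post-pregnancy rates as separate rows, keeping the post-pregnancy follow-up.
- Show pregnancies that begin after the dose separately.
- Reconcile Table 1 with section 9.4.1 and the forms in 18.1.1 and 18.1.2 by adding the LMP field to those lists.

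The cost is a wording change and one form field for a variable the protocol already lists. The during-pregnancy row will have less person-time: with even timing and full follow-up, a 24-month denominator falls by about 81% (1 − 0.19). Its confidence intervals will be correspondingly wider. The week 1 to 8 rates will hardly change.
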